3. HYPOTHESIS AND OBJECTIVE

3.1 Hypothesis:

We hypothesize that compared to usual care with the two- step screening method, CGM will increase detection of GDM and reduce maternal and neonatal adverse outcomes and health system costs related to GDM. CGM will also be shown to be highly cost-effective in preventing mother-infant dyads from developing maternal or neonatal adverse outcomes. Cost effectiveness may be achieved be either reducing maternal or neonatal health system costs without increasing the rate or heath system costs of adverse maternal or neonatal outcomes. By highly cost effective, we mean that CGM will lie within the dominant quadrant – i.e. the lower right quadrant – of the cost-effectiveness plane (Figure 1).

Figure 1. Cost Effectiveness Plane

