- Neonatal hypoglycemia defined as requiring intravenous or oral glucose
- Respiratory distress: the need for at least 4 hours of respiratory support with supplemental oxygen, continuous positive airway pressure, or ventilation at the first 24 hours of life

#UTHealth

- Fetal or neonatal death (within 28 days of birth)
- Apgar score < 7 at 5 min
- Neonatal intensive care unit (NICU) admission
- NICU length of stay
- Neonatal hypoglycemia: ≤40 mg/dL in the first 24 hours of life and less than 50 mg/dL after or requiring medical therapy
- Neonatal polycythemia defined as hematocrit (Hct) or hemoglobin (Hgb)
 level above the upper limit of normal (>2 standard deviations) for
 gestational and postnatal age.
- Neonatal hyperbilirubinemia requiring phototherapy
- Maximum bilirubin level
- Umbilical cord pH (arterial and venous)
- Need for intravenous glucose therapy
- Small for gestational age, defined as a weight below 10th percentile of the expected value according to gestational age (using the nomogram published by Duryea EL et al) (19)

Mother-Infant Dyad

- Total health system costs for mothers and infants
- Cost-effectiveness of CGM relative to usual care, assessed as the total
 incremental maternal and neonatal health system costs (savings) per
 prevented mother-infant dyad from developing a maternal adverse outcome
 (preterm birth, induction of labor, pregnancy-induced hypertension, admission
 for poor glucose control, primary cesarean section, postpartum hemorrhage,

#UTHealth

IRB NUMBER: HSC-MS-22-0153

endometritis or wound complications) or a neonatal adverse outcome (LGA, shoulder dystocia, birth injury, neonatal hypoglycemia, respiratory distress, fetal or neonatal death within 28 days of birth).

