7.2 Statistical and analysis plan

An intention to treat analysis will be conducted. All outcomes will be analyzed using generalized linear models (GLMs) and will include stratifying variables of BMI and clinic site as covariates. Primary outcome and all other binary outcomes will be analyzed with a logistic model. Secondary outcomes will be analyzed using appropriate distributional assumptions, i.e. negative binomial for counts and normal for continuous outcomes. We will report relative risks or group mean differences and 95% confidence intervals (CIs). Differences in costs will be assessed using a generalized linear model (GLM) with log-

link and gamma distribution. We will also compute the incremental cost-effectiveness ratio (ICER) of the total health system costs (savings) per prevented mother-infant dyad from developing an adverse outcome using a joint GLM with log link for costs and probit for maternal or neonatal adverse outcomes. We will induce dependency between costs and the adverse outcomes through shared random effects in the joint model.

Planned Bayesian analysis:

We will also conduct a Bayesian analysis of the primary outcome and of costs and cost-effectiveness. Sample size calculations using a Bayesian analysis with different probability thresholds are presented in Table 4. The composite primary outcome will be evaluated with a Bayesian binomial model. Finally, we conservatively set a neutral prior probability centered at a relative risk (RR) of 1.0 (*i.e.*, a priori no effect on the outcome) and a 95% credible interval of 0.3-3.3 encompassing the largest likely effect size for major outcomes in randomized trials. This neutral prior will also be used to assess cost differences between the two treatment groups. Finally, we will report RR and 95% credible intervals and the probability of reduced adverse neonatal outcomes and costs, as well as the probability that the ICER will fall in the dominant quadrant of the cost-effectiveness plane (Figure 1).

Table 4: Bayesian power to declare efficacy depending on level of evidence (probability threshold)

Control Rate	Treatment Rate	# patients /group	Prob(RR<1) > specified threshold					
			70%	75%	80%	85%	90%	95%
0.4	0.24	60	0.92	0.89	0.85	0.79	0.71	

	0.75	0.82	0.85	0.89	0.93	120	0.28	0.4
	0.90	0.93	0.96	0.98	0.98	110	0.24	0.4
	0.90	0.94	0.96	0.97	0.98	210	0.28	0.4
0.80	0.89	0.93	0.95	0.97	0.98	236	0.245	0.35
0.80	0.89	0.93	0.95	0.97	0.98	294	0.21	0.30

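### No joint cost-and-outcome summary in section 7.2 tests the weaker of section 3.1's two cost-effectiveness standards, and there is no rule for reporting a negative ICER

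*Combined protocol and SAP*

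**What the plan says.** Section 3.1 (Hypothesis) contains two statements of different strength.

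- The weaker one: "Cost effectiveness may be achieved be either reducing maternal or neonatal health system costs without increasing the rate or heath system costs". The rate and costs in question are those of adverse events in mother or infant. No margin is given for what counts as not increasing them.
- The stronger one defines highly cost-effective: "CGM will lie within the dominant quadrant – i.e. the lower right quadrant", that is, lower cost together with fewer adverse outcomes.

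Section 6.2 (Secondary outcomes, mother-infant dyad) defines the ratio as "incremental maternal and neonatal health system costs (savings) per" dyad spared an adverse outcome, where the outcome may be maternal or neonatal. Section 7.2 estimates it "using a joint GLM with log link for costs and probit for maternal or neonatal adverse outcomes", linked through shared random effects.

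The Bayesian part of section 7.2 then reports a relative risk with credible interval, "the probability of reduced adverse neonatal outcomes and costs", and "the probability that the ICER will fall in the dominant quadrant of the cost-effectiveness plane (Figure 1". The document gives no value per avoided event, no net benefit or acceptability curve, and no instruction for an ICER that is negative or has a denominator near zero.

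**The concern.** The dominance probability requires fewer adverse outcomes as well as lower cost. A trial in which CGM saves money and leaves outcomes unchanged would meet the weaker standard in section 3.1, yet no planned joint quantity would say so. Its one joint probability would sit near a coin-flip. The ICER does not help, because in the region where the hypothesis places CGM the ratio is negative and its size carries no ordering. Lower health system cost is one of the two objectives in section 3.2, so this result will be read closely.

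**Working it through.** **Notation.** dE is the reduction in the proportion of dyads with an adverse outcome, dC the cost difference (CGM minus usual care), and ICER = dC/dE. Dominant means dE > 0 and dC < 0.

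**Inputs from the document.** Control rate 25%, treated rate 17.5% (relative risk 0.7), 367 per group (section 7.1). Neutral prior centred on relative risk 1.0 with 95% interval 0.3 to 3.3 (section 7.2).

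**Assumptions.** The document gives no dyad composite rate, cost mean, cost SD or cost-effect correlation. I took composite rates of 25% to 75%, applied the same prior to the composite, and chose cost figures for illustration only.

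**1. Reproduce Table 4 (0.25 vs 0.175, 367 per group).**
- Prior SD of log RR = (ln 3.3 − ln 0.3)/(2 × 1.96) = 0.61.
- Variance of log RR = 0.75/(367 × 0.25) + 0.825/(367 × 0.175) = 0.0210, so SE = 0.145.

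| Threshold | 70% | 75% | 80% | 85% | 90% | 95% |
|---|---|---|---|---|---|---|
| Table 4 | 0.98 | 0.97 | 0.95 | 0.93 | 0.89 | 0.80 |
| Recomputed | 0.975 | 0.965 | 0.948 | 0.923 | 0.878 | 0.785 |

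All agree within 2 points, so the posterior model below matches the plan's.

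**2. Equal outcomes, saving certain.** P(dominant) cannot exceed P(dE > 0).
- With true RR = 1, P(RR < 1) = Φ(√w · z), where z is standard normal and w = prior variance/(prior variance + sampling variance).
- At 25% and 367 per group the sampling variance is 2 × 0.75/(0.25 × 367) = 0.0163, so w = 0.374/(0.374 + 0.016) = 0.96.
- By symmetry the mean is 0.50. Sample size enters only through w, which tends to 1, so a larger trial does not move it.
- Simulation at every rate from 25% to 75%: mean 0.50; above 0.75 in 24–25% of trials, above 0.90 in about 10%, above 0.95 in about 5%. At 408 per group the results are the same.

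**3. Equal outcomes, saving uncertain.**
- True saving of 2.8 standard errors: P(saving) averages Φ(2.8/√2) = 0.976, and P(dominant) averages 0.5 × 0.976 = 0.49.
- Savings of 2.5 to 4 standard errors with correlation 0 to 0.3: P(dominant) averages 0.48–0.50 and exceeds 0.90 in 7–10% of trials, while P(saving) averages 0.96–0.998.

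**4. Outcomes not equal.**
- RR 0.7 at a 25% rate: P(dominant) averages 0.96 with the saving certain and 0.94 with a saving of 2.8 standard errors.
- RR 0.95, 408 per group, saving certain: 0.62, 0.66, 0.73 and 0.80 at composite rates of 25%, 40%, 60% and 75%.

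**5. A direct measure of the weaker standard.** Mean P(RR < 1 + m) when true RR = 1, 367 per group, for assumed margins m:

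| Composite rate | m = 5% | m = 10% | m = 20% |
|---|---|---|---|
| 25% | 0.61 | 0.71 | 0.85 |
| 60% | 0.72 | 0.87 | 0.98 |

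If cost and effect are independent and the saving is 2.8 standard errors, multiply by 0.976. Unlike P(dominant), these rise with sample size.

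**6. The ratio itself.** Illustrative costs in dollars; net benefit = λ·dE − dC at λ = 20,000.

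| dE | dC | ICER | Net benefit |
|---|---|---|---|
| +0.075 | −750 | −10,000 | +2,250 |
| −0.075 | +750 | −10,000 | −2,250 |
| +0.15 | −750 | −5,000 | +3,750 |
| +0.075 | −1,500 | −20,000 | +3,000 |

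Rows 1 and 2 are opposite results with the same ICER. Rows 3 and 4 both improve on row 1, but the ratio moves in opposite directions.

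Near zero effect, take true dE = 0 with SD √(2 × 0.25 × 0.75/367) = 0.032, and dC = −1,000 with SD 510. The central 95% of ICER draws runs from about −500,000 to +510,000, and the draws split 49% lower right and 49% lower left.

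**7. Net benefit in the equal-outcome case.** Take a saving of 1,000 with SE 357 (2.8 standard errors) and 367 per group. The mean probability of positive net benefit is Φ(1,000/(√2 · √(357² + (0.032λ)²))) at a 25% rate.
- λ = 0: 0.98.
- λ = 10,000: 0.93 (0.92 at a 60% rate).
- λ = 20,000: 0.83 (0.81 at a 60% rate).

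The curve shows where the case for CGM is strong and where it weakens.

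**The case against.** Four stronger readings are tempting, and the document does not support them.

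- A reader might infer that section 7.2 offers nothing beyond the ICER and the dominance probability. It also reports a relative risk and the probabilities that neonatal events and costs fall, and it fits a cost model. On the natural reading the probability of a saving, which is the zero point of an acceptability curve, is already planned. These are marginal statements, however, and the outcome one concerns the neonatal composite, while the ICER uses maternal or neonatal events. They cannot be combined into the missing joint statement. If the phrase were instead read as one joint probability, it would again require fewer events and meet the same ceiling.
- A reader might infer that the dominance probability is the wrong test. It is the right test of the highly cost-effective hypothesis. If outcomes are equal, dominance does not hold and a value near 0.5 is a fair posterior. The gap is that the weaker standard has no test of its own. The weaker sentence is incomplete in grammar and may describe a route rather than a formal hypothesis, but it does say what would count as cost-effective.
- A reader might infer that the planned output cannot separate dominant from dominated results. A quadrant probability computed on the cost-effect pair has no sign ambiguity. The ambiguity is confined to the numeric ICER and any interval around it.
- A reader might infer that net benefit should replace the sponsor's summary. That would be a preference, and it needs a value for a composite running from induction of labor to death, which the document does not supply.

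It is also fair to say that costs and cost-effectiveness are secondary outcomes in section 6.2, that no decision threshold is attached to them, and that neither the design nor the data collection is affected.

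**Conclusion.** The point holds in a limited form. Section 3.1 sets two cost-effectiveness standards, and the joint summaries in section 7.2 test only the stronger. With lower cost and equal outcomes, the dominance probability averages 0.48 to 0.50 whatever the trial size. With a small true benefit (RR 0.95) it is moderate, about 0.62 to 0.80 depending on the composite rate, and in that case it would rise with sample size. At RR 0.7 it performs well. Separately, the numeric ICER cannot be ranked where the hypothesis lies, takes the same values in the dominated quadrant, and is unstable near zero effect.

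The 0.5 result follows from symmetry and does not depend on the cost inputs, provided the prior is neutral. The other probabilities rest on assumed composite rates, savings, correlations and margins, and RR 0.7 is planned for the neonatal outcome and only assumed to carry over to the dyad composite. This is an inexpensive improvement to the analysis plan and leaves the primary clinical outcome untouched.

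**What to change.** In section 7.2, keep the dominance probability as the test of the highly cost-effective hypothesis. From the same joint posterior draws of dE and dC, using the dyad composite, add:

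- (a) the probabilities of all four quadrants;
- (b) incremental net benefit and an acceptability curve over a prespecified range of value per avoided adverse-outcome dyad, starting at zero dollars;
- (c) the joint probability that cost is lower and the dyad composite is not worse by more than a margin stated by the sponsor, which is the direct test of the weaker standard;
- (d) a reporting rule: give a numeric ICER only when dC and dE have the same sign, and otherwise state dominant or dominated.

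State also that the probabilities of fewer neonatal events and of lower cost are two separate quantities.

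The cost is SAP wording and a few further summaries of draws already planned, with no new data. The real burden is that the sponsor must choose and justify a value range and a margin before seeing results. The values used here are illustrations, not proposals.

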7.3 Ancillary Studies

- 1. Satisfaction survey: All participants will be given a short, anonymized survey after completing their screening test. The aim of the survey is to assess participant satisfaction with the screening method they received and care provided throughout study period. The survey will take less than five minutes to complete. The survey will be scored in a Likert-type scale allowing for results to undergo descriptive analysis.
- 2. Procedure specific satisfaction surveys: We would like to administer a satisfaction survey specific to each screening arm: routine care and CGM placement. Participants will be given a short, anonymized survey after completing their screening test. The aim of the survey is to assess participant's experience, perception and satisfaction with the 2-step glucose tests and CGM application. The surveys will take less than five minutes to complete. The surveys will be scored in a Likert-type scale allowing for results to undergo descriptive analysis.

- 3. Pre-specified secondary analysis: We have planned for a pre-specified secondary analysis after completion of data analysis. There are as follows:
 - Blood sugars using blinded CGM with 1-hour GCT results and composite maternal and adverse outcomes.
 - Evaluation of one-hour screening GCT threshold and composite maternal and adverse outcomes.
 - Evaluation of one abnormal value during 3-hour GTT and composite maternal and adverse outcomes.
 - Risk factors and adverse outcomes associated with ultrasound diagnosed large for gestational age fetus.
 - Risk factors and adverse outcomes associated with large for gestational age neonates.
 - Fetal growth or amniotic fluid abnormalities during third trimester ultrasound exam among GDM.
 - Gestational diabetic outcomes with and without Hypertensive Disorder of Pregnancy.
 - Compliant versus non-compliant gestational diabetic: risk factors and associated adverse outcomes.
 - The racial and ethnic disparity among gestational diabetics.
 - Risk factors associated with neonatal hypoglycemia.
 - Evaluation of time above range using CGM and associated neonatal outcomes.

 Maternal hypoglycemia using CGM and composite maternal and adverse outcomes.

Maternal breastfeeding and diabetes status and associated maternal and

neonatal outcomes.

Maternal breastfeeding, obesity and diabetes status and associated maternal

and neonatal outcomes.

Maternal breastfeeding and CGM glycemic profile and associated maternal

and neonatal outcomes.

• Incremental cost for prevention of Type II DM in life using a model method.

7.4 Feasibility

Our clinics see greater than 250 people a week and approximately 6,000 deliveries

at our four participating centers. We aim to enroll about ten people per week, based on

the previous prospective CGM in pregnancy study. Assuming 10% of people will decline

to participate, we will expect to recruit 816 people in 2 years.

8. SAFETY MEASUREMENTS

8.1 Definitions

Serious adverse events will be monitored throughout the study, though not

anticipated.

8.2 Procedures for safety monitoring

A review of available experimental and observational literature has shown benefit in

outcomes associated with CGM use in pregnant and non-pregnant people with the

minimal risk associated with the device (20).

#UTHealth IRB N

IRB NUMBER: HSC-MS-22-0153 IRB APPROVAL DATE: 07/05/2023

9. ETHICAL CONSIDERATIONS

9.1 Informed consent

All study candidates will be given a full explanation of the study procedure and allowed to read the entire consent form. In addition, they will be given an opportunity to ask any questions. After all, questions have been answered, and the Investigator is confident that the participant understands the requirements of the study, the participant will sign the consent form. In addition, the participant will receive a copy of the informed consent.

9.2 Institutional review board

The Principal Investigator will obtain approval of the research protocol from the IRB.

Per U.S. law, the study will be registered in www.clinicaltrials.gov for public access.

9.3 Subject confidentiality

A study number will be assigned to each participant prior to collecting the data. This will maintain the subject's anonymity as they will be de-identified. There will be a record of the participants at the study site to each assigned study number.

The research staff completed the required Collaborative Institution Training Initiative (CITI Training). Access to personal information will be limited to investigators only.

Therefore, they are required to keep all information confidential.

In addition, Electronic Medical Record, *Epic*, will be used for pre-screening of individual characteristics. Once identified, participant will be approached via EPIC secured portal messaging system and/or contacted via phone for presentation of research study. If interested, individual will be scheduled a research portal visit.

#UTHealth Houston IRB NUMBER: HSC-MS-22-0153
IRB APPROVAL DATE: 07/05/2023

A secure research portal created by University of Texas, Houston *Epic* Personnel will maintain a screening and actively enrolled participant list. Access will only be granted to those included on the IRB.

The participants will be de-identified when data is reported in any format, including but not limited to medical journals or scientific meetings.

10. DATA HANDLING AND RECORD-KEEPING

10.1 Access to source documents

Research personnel will perform data collection through the abstraction of participant electronic medical records from multiple sites. Demographics, variables, and outcomes will be collected and entered into a Redcap database and the Dexcom data capture platform. Attached to this protocol is a detailed list of variables that will be collected. Data will be obtained from randomization up until 6 weeks postpartum.

10.2 Records Retention:

Data will be collected and de-identified in the UTHealth Redcap system. At the time of study completion, approved protocol and all other supporting documents pertaining to the project will be retained. Data will be de-identified and available for future analysis. Following completion of the study and analysis of data, the de-identified data will be shared to Dexcom Inc.

10.3 Quality control assurance

The Principal Investigator and co-investigators will go through all the files to verify that the data is reliable and complete. Verification will be completed through assessment by Principal Investigator and co-investigator.

#UTHealth IRI

IRB NUMBER: HSC-MS-22-0153 IRB APPROVAL DATE: 07/05/2023

